3.2 Post Study Access to Therapy

At the conclusion of the study, subjects who continue to demonstrate clinical benefit will be eligible to receive study drug, except for Cohort B subjects who did not progress during the 5 year follow-up (4 years from randomization). Study drug will be provided via an extension of the study, a rollover study requiring approval by responsible health authority and ethics committee or through another mechanism at the discretion of BMS. BMS reserves the right to terminate access to study drug if any of the following occur: a) the marketing application is rejected by responsible health authority; b) the study is terminated due to safety concerns; c) the subject can

obtain medication from a government sponsored or private health program; or d) therapeutic alternatives become available in the local market.

3.3 Study Population

For entry into the study, the following criteria MUST be met.

3.3.1 Inclusion Criteria

1. Signed Written Informed Consent

- a) Subjects must have signed and dated an IRB/IEC approved written informed consent form in accordance with regulatory and institutional guidelines. This must be obtained before the performance of any protocol related procedures that are not part of normal subject care.
- b) Subjects must be willing and able to comply with scheduled visits, treatment schedule, laboratory tests and other requirements of the study.

2. Target Population

- a) Subjects with histologically- or cytologically-documented NSCLC (SQ or NSQ) who present with Stage IIIB/Stage IV disease (according to version 7 of the International Association for the Study of Lung Cancer Staging Manual in Thoracic Oncology), or with recurrent or progressive disease following multimodal therapy (radiation therapy, surgical resection, or definitive chemoradiotherapy for locally advanced disease).
- b) Subjects must have experienced disease progression or recurrence during or after at least one systemic therapy for advanced or metastatic disease.
 - i) Each subsequent line of therapy must be preceded by disease progression. A switch of an agent within a regimen in order to manage toxicity does not define the start of a new line of therapy.
 - ii) Maintenance therapy following platinum doublet-based chemotherapy is not considered as a separate regimen of therapy.
 - iii) Subjects who received platinum-containing adjuvant, neoadjuvant or definitive chemoradiation therapy given for locally advanced disease, and developed recurrent (local or metastatic) disease within 6 months of completing therapy are eligible.
 - iv) Subjects with recurrent disease > 6 months after completing a platinum-containing adjuvant, neoadjuvant or definitive chemoradiation therapy given for locally advanced disease, who also subsequently progressed during or after a systemic regimen given to treat the recurrence, are eligible.
 - v) Subjects with non-squamous histology must be tested for EGFR mutations (including, but not limited to, deletions in exon 19 and exon 21 [L858R] substitution) and ALK rearrangement if tests have not been previously performed.
 - EGFR testing is not required if ALK or KRAS test is positive.
 - ALK testing is not required if EGFR or KRAS test is positive.

Subjects who are positive on sensitizing EGFR mutations (exon 19 deletion, exon 21 mutation (L858R)) or ALK rearrangement testing, are eligible to enroll after progression from first line tyrosine kinase inhibitor (TKI) regimen.

Subjects who are positive on nonsensitizing EGFR mutation are eligible to enroll after one line of systemic therapy, which can be either TKI or chemotherapy.

Subjects are eligible if genetic test results are indeterminate or if no tumor tissue is available or accessible for testing as long as they have received one prior systemic chemotherapy.

- vi) Experimental therapies when given as separate regimen are considered as separate line of therapy.
- c) Subjects must have measurable disease by CT or MRI per RECIST 1.1 criteria (radiographic tumor assessment performed within 28 days of first dose of study drug) or clinically apparent disease that the investigator can follow for response per RECIST 1.1.
- d) Eastern Cooperative Oncology Arm (ECOG) performance status (PS)
 - i) PS 0 to 1
 - ii) PS 2 Subgroup 4 ([Table 3.1-1](#)) only)
- e) All baseline laboratory requirements will be assessed and should be obtained within 14 days (unless otherwise specified in [Table 5.1-1](#)) of first dose of study drug. Screening laboratory values must meet the following criteria
 - i) WBCs > 2000/ μ L
 - ii) Neutrophils > 1500/ μ L
 - iii) Platelets > 100 x 10³/ μ L
 - iv) Hemoglobin > 9.0 g/dL
- v) Serum creatinine of < 1.5 X ULN (upper limit of normal) or creatinine clearance > 40 mL/minute (using Cockcroft/Gault formula)
Female CrCl=
$$\frac{(140 - \text{age in years}) \times \text{weight in kg} \times 0.85}{72 \times \text{serum creatinine in mg/dL}}$$

Male CrCl=
$$\frac{(140 - \text{age in years}) \times \text{weight in kg} \times 1.00}{72 \times \text{serum creatinine in mg/dL}}$$
- vi) AST < 3X ULN
- vii) ALT < 3X ULN
- viii) Total bilirubin < 1.5X ULN (except subjects with Gilbert Syndrome who must have total bilirubin < 3.0 mg/dL)
- f) Prior radiotherapy or radiosurgery must have been completed at least 2 weeks prior to starting study treatment
- g) Subject Re-enrollment: This study permits the re-enrollment of a subject that has discontinued the study as a pretreatment failure (ie, subject has not been randomized / has not been treated). If re-enrolled, the subject must be re-consented.

3. Age and Reproductive Status

- a) Men and women, ages \geq 18 years, inclusive
- b) Women of childbearing potential (WOCBP) must have a negative serum or urine pregnancy test (minimum sensitivity 25 IU/L or equivalent units of HCG) within 24 hours prior to the start of study drug.
- c) Women must not be breastfeeding
- d) WOCBP must agree to follow instructions for method(s) of contraception for the duration of treatment with nivolumab plus 5 months post-treatment completion. The methods of contraception are outlined in [Appendix 03](#).
- e) Men who are sexually active must adhere to the contraception requirements for male subjects for the duration of treatment with nivolumab plus 7 months post-treatment completion per [Appendix 03](#). Female partners, who are WOCBP, of male subjects who are sexually active, must agree to follow instructions for method(s) of contraception for the duration of treatment with nivolumab plus 7 months post-treatment completion. The methods of contraception are outlined in [Appendix 03](#).

Investigators shall counsel WOCBP and male subjects who are sexually active with WOCBP on the importance of pregnancy prevention and the implications of an unexpected pregnancy. Investigators shall advise WOCBP and male subjects who are sexually active with WOCBP on the use of highly effective methods of contraception.

3.3.2 *Exclusion Criteria*

1. Target Disease Exceptions

- a) Subjects with active CNS metastases are excluded. Subjects are eligible if the CNS metastases are adequately treated and subjects are neurologically returned to baseline (except for residual signs or symptoms related to the CNS treatment) for at least 2 weeks prior to enrollment. In addition, subjects must be either off corticosteroids, or on a stable or decreasing dose of < 10 mg daily prednisone (or equivalent).
- b) Subjects with carcinomatous meningitis.

2. Medical History and Concurrent Diseases

- a) Subjects with a history of interstitial lung disease (eg, sarcoidosis) that is symptomatic or may interfere with the detection or management of suspected drug-related pulmonary toxicity. Subjects with COPD whose disease is controlled at study entry are allowed.
- b) Subjects with active, known or suspected autoimmune disease. Subjects with type I diabetes mellitus, hypothyroidism only requiring hormone replacement, skin disorders (such as vitiligo, psoriasis or alopecia) not requiring systemic treatment, or conditions not expected to recur in the absence of an external trigger are permitted to enroll.
- c) Subjects with a condition requiring systemic treatment with either corticosteroids (> 10 mg daily prednisone equivalent) or other immunosuppressive medications within 14 days of first dose of study drug. Inhaled or topical steroids, and adrenal replacement steroid doses > 10 mg daily prednisone equivalent, are permitted in the absence of active autoimmune disease.

- d) Subjects who participated in either arm of the following clinical trials CA209-017, CA209-057, CA209-026, and CA184-104 or received prior treatment with anti-PD-1 or anti-PDL1 experimental agents.
- e) Subjects with a history of screen failure to any PD1 or PDL1 antibody clinical trial due to PDL1 status.
- f) Subjects with previous malignancies (except non-melanoma skin cancers, and the following in situ cancers: bladder, gastric, colon, endometrial, cervical/dysplasia, melanoma, or breast) are excluded unless a complete remission was achieved at least 2 years prior to study entry AND no additional therapy are ongoing and required during the study period with the exception of anti-estrogen/androgen therapy or bisphosphonates. Subjects with other active malignancy requiring concurrent intervention are excluded.
- g) All toxicities attributed to prior anti-cancer therapy other than alopecia, fatigue, or peripheral neuropathy must have resolved to Grade 1 (NCI CTCAE version 4) or baseline before administration of study drug.
- h) Subjects must have recovered from the effects of major surgery or significant traumatic injury at least 14 days before the first dose of study treatment.

3. Physical and Laboratory Test Findings

- a) Any positive test for Hepatitis B virus or Hepatitis C virus indicating acute or chronic infection.
- b) Known history of testing positive for Human Immunodeficiency Virus (HIV) or Acquired Immunodeficiency Syndrome (AIDS).

4. Allergies and Adverse Drug Reaction

- a) History of severe hypersensitivity reactions to other monoclonal antibodies.
- b) History of allergy or intolerance (unacceptable adverse event) to study drug components or Polysorbate-80-containing infusions.

5. Sex and Reproductive Status

- a) WOCBP who are pregnant or breastfeeding
- b) Women with a positive pregnancy test at enrollment or prior to administration of study medication

6. Prohibited Treatments and/or Restricted Therapies

- a) Ongoing or planned administration of anti-cancer therapies other than those specified in this study
- b) Use of corticosteroids or other immunosuppressive medications as per [Section 3.4.1](#)
- c) An exclusion criterion has been deleted. The numbering of subsequent criteria is maintained.
- d) Treatment with any investigational agent within 14 days of first administration of study treatment

7. Other Exclusion Criteria

- a) Any other serious or uncontrolled medical disorder, active infection, physical exam finding, laboratory finding, altered mental status, or psychiatric condition that, in the opinion of the investigator, would limit a subject's ability to comply with the study requirements, substantially increase risk to the subject, or impact the interpretability of study results
- b) Prisoners or subjects who are involuntarily incarcerated
- c) Subjects who are compulsorily detained for treatment of either a psychiatric or physical (eg, infectious disease) illness.

Eligibility criteria for this study have been carefully considered to ensure the safety of the study subjects and that the results of the study can be used. It is imperative that subjects fully meet all eligibility criteria.

3.3.3 ***Women of Childbearing Potential***

A Women of childbearing potential (WOCBP) is defined as any female who has experienced menarche and who has not undergone surgical sterilization (hysterectomy or bilateral oophorectomy) and is not postmenopausal. Menopause is defined as 12 months of amenorrhea in a woman over age 45 years in the absence of other biological or physiological causes. In addition, women under the age of 55 years must have a serum follicle stimulating hormone, (FSH) level $> 40\text{mIU/mL}$ to confirm menopause.*

*Women treated with hormone replacement therapy, (HRT) are likely to have artificially suppressed FSH levels and may require a washout period in order to obtain a physiologic FSH level. The duration of the washout period is a function of the type of HRT used. The duration of the washout period below are suggested guidelines and the investigators should use their judgment in checking serum FSH levels. If the serum FSH level is $>40\text{ mIU/ml}$ at any time during the washout period, the woman can be considered postmenopausal:

- 1 week minimum for vaginal hormonal products (rings, creams, gels)
- 4 week minimum for transdermal products
- 8 week minimum for oral products

Other parenteral products may require washout periods as long as 6 months.

3.4 **Concomitant Treatments**

3.4.1 ***Prohibited and/or Restricted Treatments***

The following medications are prohibited during the study (unless utilized to treat a drug related adverse event):

- Immunosuppressive agents (except to treat a drug-related adverse event)
- Immunosuppressive doses of systemic corticosteroids (except as stated in [Section 3.4.3](#))
- Any concurrent antineoplastic therapy (ie, chemotherapy, hormonal therapy, immunotherapy, extensive, non-palliative radiation therapy, or standard or investigational agents for treatment of NSCLC).

- Any botanical preparation (eg, herbal supplements or traditional Chinese medicines) intended to treat the disease under study or provide supportive care.

Prior radiotherapy must have been completed at least 2 weeks prior to starting study treatment per inclusion criteria 2g. See Section 3.4.3 for guidance on concomitant palliative radiotherapy.

3.4.2 Other Restrictions and Precautions

Subjects with active, known or suspected autoimmune disease are excluded. Subjects with type I diabetes mellitus, hypothyroidism only requiring hormone replacement, skin disorders (such as vitiligo, psoriasis, or alopecia) not requiring systemic treatment, or conditions not expected to recur in the absence of an external trigger are permitted to enroll.

Subjects with a condition requiring systemic treatment with either corticosteroids (> 10 mg daily prednisone equivalent) or other immunosuppressive medications within 14 days of starting treatment are excluded. Inhaled or topical steroids, and adrenal replacement steroid doses > 10 mg daily prednisone equivalent, are permitted in the absence of active autoimmune disease.

3.4.3 Permitted Therapy

Subjects are permitted the use of topical, ocular, intra-articular, intranasal, and inhalational corticosteroids (with minimal systemic absorption). Adrenal replacement steroid doses > 10 mg daily prednisone are permitted. A brief (less than 3 weeks) course of corticosteroids for prophylaxis (eg, contrast dye allergy) or for treatment of non-autoimmune conditions (eg, delayed-type hypersensitivity reaction caused by a contact allergen) is permitted.

Concomitant palliative and supportive care for disease related symptoms (including bisphosphonates and RANK-L inhibitors) is allowed if initiated prior to first dose of study therapy.

The potential for overlapping toxicities with radiotherapy and nivolumab currently is not known. Therefore, palliative radiotherapy is not recommended while receiving nivolumab. If palliative radiotherapy is required, then nivolumab should be withheld for at least 1 week before, during, and 1 week after radiation. Subjects should be closely monitored for any potential toxicity during and after receiving radiotherapy, and AEs should resolve to Grade ≤ 1 prior to resuming nivolumab. Only non-target bone lesions that do not include lung tissue in the planned radiation field may receive palliative radiotherapy. Details of palliative radiotherapy should be documented in the source records and electronic case report form (eCRF). Details in the source records should include: dates of treatment, anatomical site, dose administered and fractionation schedule, and adverse events. Subjects receiving limited field palliative radiation therapy will be considered to have unequivocal progression of disease in the non-target lesion. Symptoms requiring palliative radiotherapy should be evaluated for objective evidence of disease progression. Administration of additional nivolumab to subjects who received limited field palliative radiation should follow guidelines specified in [Section 4.3.4](#), Treatment beyond Disease Progression.

3.5 Discontinuation of Subjects from Treatment

Subjects MUST discontinue investigational product (and non-investigational product at the discretion of the investigator) for any of the following reasons:

- Subject's request to stop study treatment
- Any clinical adverse event (AE), laboratory abnormality or intercurrent illness which, in the opinion of the investigator, indicates that continued participation in the study is not in the best interest of the subject
- Pregnancy
- Termination of the study by Bristol-Myers Squibb (BMS)
- Loss of ability to freely provide consent through imprisonment or involuntarily incarceration for treatment of either a psychiatric or physical (eg, infectious disease) illness
- After randomization in Cohort B, until disease progression when subjects are eligible for retreatment
- Other protocol specific reasons for discontinuation as specified in [Section 4.3.5](#).

All subjects who discontinue investigational product should comply with protocol specified follow-up procedures as outlined in [Section 5](#). Subjects in Cohort B continue with the on-study visit schedule ([Table 5.1-2](#)) until disease progression following retreatment or upon a decision to not receive retreatment, unacceptable toxicity, or withdrawal of informed consent. The only exception to this requirement is when a subject withdraws consent for all study procedures including post-treatment study follow-up or loses the ability to consent freely (ie, is imprisoned or involuntarily incarcerated for the treatment of either a psychiatric or physical illness).

If study treatment is discontinued prior to the subject's completion of the study, the reason for the discontinuation must be documented in the subject's medical records and entered on the appropriate case report form (CRF) page.

3.6 Post Treatment Study Follow up

Subjects who discontinue study treatment will continue to be followed. The subjects will be followed up for select AEs beyond 100 days from the last dose of study therapy, for ongoing drug-related AEs until resolved, return to baseline or deemed irreversible, or until lost to follow-up or withdrawal of study consent.

One of the exploratory end points is overall survival and every attempt will be made to obtain survival status every 3 months until death, lost to follow-up, or withdrawal of study consent.

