Adverse Events Assessment	X	X	*Beyond 100 days from the last dose of study therapy, subjects will be followed for ongoing drug-related AEs until resolved, return to baseline or deemed irreversible, or until lost to follow-up or withdrawal of study consent.

Table 5.1-3: Follow-up Procedural Outline (CA209153)

Procedure	Initial Follow-Up Phase (100 days from the date of last study treatment) Follow-up Visit 1 (X01) and Visit 2 (X02)	Further Follow-up Phase (beyond X02)	Notes 
 • Subjects who discontinue treatment prior to randomization and subjects in Cohort A: Follow-up Visit 1 (X01) is to occur 30 days (\pm 5 days) after last dose or coinciding with the date of discontinuation (\pm 5 days) if date of discontinuation is greater than 35 days after last dose. • Subjects in Cohort B: Follow-up Visit 1 (X01) is to occur 30 days (\pm 5 days) after disease progression and a decision has been made to not retreat the subject or at 30 days (\pm 5 days) of discontinuation after retreatment • Follow up Visit 2 (X02) is to occur approximately 70 days (\pm 5 days) after X01
Laboratory Tests	X		CBC with differential, serum chemistry (BUN or serum urea level, serum creatinine, albumin, sodium, potassium, calcium, magnesium, phosphate, chloride, glucose), liver function (AST, ALT, total bilirubin, alkaline phosphatase, LDH), thyroid function (TSH, reflex to free T3 and free T4 if abnormal result)
Review of concomitant medications	X		
Pregnancy testing	X		
EQ-5D	X	X	Beyond 100 days from the last dose of study therapy, the EQ-5D will be administered every 3 months for the first 12 months, then every 6 months thereafter, as permitted by local IRB
Collection of Survival Information	X	X	Every 3 months until death, lost to follow-up, or withdrawal of study consent for 5 years following start of therapy. May be performed by phone contact or office visit.

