- admission encountered for another life circumstance that carries no bearing on health status and requires no medical/surgical intervention (eg, lack of housing, economic inadequacy, caregiver respite, family circumstances, administrative reason).

6.1.1 *Serious Adverse Event Collection and Reporting*

Following the subject's written consent to participate in the study, all SAEs, whether related or not related to study drug, must be collected, including those thought to be associated with protocol-specified procedures. All SAEs must be collected that occur during the screening period and within 100 days of discontinuation of dosing. If applicable, SAEs must be collected that relate to any later protocol-specified procedure (eg, a follow-up skin biopsy).

The investigator should report any SAE that occurs after these time periods and that is believed to be related to study drug or protocol-specified procedure.

An SAE report should be completed for any event where doubt exists regarding its seriousness.

If the investigator believes that an SAE is not related to study drug, but is potentially related to the conditions of the study (such as withdrawal of previous therapy or a complication of a study procedure), the relationship should be specified in the narrative section of the SAE Report Form.

SAEs, whether related or not related to study drug, and pregnancies must be reported to BMS (or designee) within 24 hours. SAEs must be recorded on the SAE Report Form; pregnancies on a Pregnancy Surveillance Form (electronic or paper forms). When using paper forms, the reports are to be transmitted via email or confirmed facsimile (fax) transmission to:

SAE Email Address: Refer to Contact Information list.

SAE Facsimile Number: Refer to Contact Information list.

For studies capturing SAEs through electronic data capture (EDC), electronic submission is the required method for reporting. The paper forms should be used and submitted immediately, only

in the event the electronic system is unavailable for transmission. When paper forms are used, the original paper forms are to remain on site.

SAE Telephone Contact (required for SAE and pregnancy reporting): Refer to Contact Information list.

If only limited information is initially available, follow-up reports are required. (Note: Follow-up SAE reports should include the same investigator term(s) initially reported.)

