6.2.1 Nonserious Adverse Event Collection and Reporting

The collection of nonserious AE information should begin at initiation of study drug. Nonserious AE information should also be collected from the start of a placebo lead-in period or other observational period intended to establish a baseline status for the subjects.

Nonserious AEs should be followed to resolution or stabilization, or reported as SAEs if they become serious (see [Section 6.1.1](#)). Follow-up is also required for nonserious AEs that cause interruption or discontinuation of study drug and for those present at the end of study treatment as appropriate. All identified nonserious AEs must be recorded and described on the nonserious AE page of the CRF (paper or electronic).

Completion of supplemental CRFs may be requested for AEs and/or laboratory abnormalities that are reported/identified during the course of the study.

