8.3.2 Secondary Endpoint(s)

The secondary objective of the study will be assessed by measuring the following:

- incidence for high grade (Grade 3-4 and Grade 5) select adverse events
- median time to onset, median time to resolution (Grade 3-4)
- percentage of subjects who received immune modulating medication (e.g. corticosteroids, infliximab, cyclophosphamide, IVIG, and mycophenolate mofetil), or hormonal replacement therapy, the percentage of subjects who received ≥ 40 mg prednisone equivalents, total duration of all immune modulating medications given for the select event.

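### After day 100, Table 5.1-3 follows only drug-related AEs, so outcomes of not-related high-grade select AEs that the secondary objective needs may go unrecorded

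*Combined protocol and SAP*

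**What the plan says.** Here day 100 means 100 days after the last dose of study drug.

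- **Section 3.6** opens with "The subjects will be followed up for select AEs beyond 100 days from the last dose of study therapy". The same sentence continues "for ongoing drug-related AEs until resolved, return to baseline or deemed irreversible, or until lost to follow-up or withdrawal of study consent". The syntax does not show whether the second part adds to the first or defines it.
- **Table 5.1-3**, Adverse Events Assessment row, marks AE assessment in both follow-up phases, but its note reads "Beyond 100 days from the last dose of study therapy, subjects will be followed for ongoing drug-related AEs until resolved". It mentions neither select AEs nor new-onset events.
- **Section 6.1.1** sets the routine window: "All SAEs must be collected that occur during the screening period and within 100 days of discontinuation of dosing". For later events it adds "The investigator should report any SAE that occurs after these time periods and that is believed to be related to study drug". It also requires SAEs to be followed until resolved or stable, with no limit to related events.
- **Section 6.2.1** says "Nonserious AEs should be followed to resolution or stabilization", again whatever the cause. It gives a start for nonserious AE collection but no end.
- **Sections 1.3.2 and 8.3.2** define the secondary objective as incidence and outcome of all high-grade select AEs. The endpoints are "incidence for high grade (Grade 3-4 and Grade 5) select adverse events", time to onset, time to resolution (Grade 3-4) and use of immune-modulating medication. Relationship to drug is not a condition.
- **Sections 8.4.2 and 8.4.3** state no time window for incidence. Section 8.4.3 censors an unresolved event at the last contact date.

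**The concern.** The rule for what is recorded after day 100 differs between the visit schedule, which sites work from, and the text on adverse events. The difference turns on relationship to drug, which the secondary objective deliberately leaves out. That matters here because Sections 1.1 and 1.4.3.2 say that drug-related and unrelated causes of pulmonary findings can be hard to tell apart in NSCLC.

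If the table is followed, outcome data beyond day 100 exist only for events judged related. A not-related Grade 3-4 event that is open at day 100 gets no end date. It then stays in the Kaplan-Meier risk set as unresolved up to the last contact, although nobody is asking about it. That pushes the estimated time to resolution upward.

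**Working it through.** **Step 1. Passages side by side, by event type (high-grade select AEs after day 100).**

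| Event | 3.6, broad reading | Table 5.1-3 | Section 6 | What is uncertain |
|---|---|---|---|---|
| Ongoing, related | followed | followed | followed | nothing |
| Ongoing, not related | followed | not followed | followed to resolution or stabilization | outcome (secondary) |
| New, related, serious | followed | not named | reportable, no time limit | nothing for the primary |
| New, related, nonserious Grade 3-4 | followed | not named | no end date; recorded if identified | primary and secondary incidence |
| New, not related, serious | followed | not named | outside 6.1.1 unless tied to a protocol procedure | secondary incidence |
| New, not related, nonserious | followed | not named | no end date; recorded if identified | secondary incidence |

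A high-grade event already open at day 100 began earlier and is already in the incidence numerator. Only its outcome is at risk.

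**Step 2. How far censoring can run.** Survival contacts are every 3 months for 5 years from the start of therapy (Table 5.1-3). Take a subject not in Cohort B whose last dose falls at 52 weeks:

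- 5 x 365 = 1,825 days of survival follow-up
- 52 x 7 = 364 days on treatment
- 1,825 - 364 - 100 = 1,361 days

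An event left open at day 100 could count as unresolved for up to 1,361 further days with no information on its status.

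**Step 3. The plan's own precision figures.** Table 8.1-1 uses exact intervals. The Clopper-Pearson limits are the 0.025 quantile of Beta(x, n-x+1) and the 0.975 quantile of Beta(x+1, n-x).

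- 4/780 = 0.51%, 95% CI 0.14% to 1.31%
- 16/780 = 2.05%, 95% CI 1.18% to 3.31%

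Both match the plan, as do all 16 rows of the table.

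**Step 4. Size of the new-onset gap (illustrative).** The documents give no share of select AEs starting after day 100, so the shares here are assumptions. The 5% base is the Grade 3-4 treatment-related rate in the 129 NSCLC subjects of the Phase 1 study (Section 1.1), applied to 1,280 treated subjects.

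- 5% x 1,280 = 64 events
- 2% x 64 = 1.3 and 10% x 64 = 6.4, so about 1 to 6 subjects
- In a category at 0.5%: 0.005 x 1,280 = 6.4, so one event is about a sixth of the estimate

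If up to 25% of events were missed:

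| N | Complete count | 10% missed | 25% missed |
|---|---|---|---|
| 780 | 16: 2.05% (1.18-3.31) | 14: 1.79% (0.98-2.99) | 12: 1.54% (0.80-2.67) |
| 1,280 | 26: 2.03% (1.33-2.96) | 23: 1.80% (1.14-2.68) | 20: 1.56% (0.96-2.40) |
| 1,280 | 6: 0.47% (0.17-1.02) | 5: 0.39% (0.13-0.91) | 4: 0.31% (0.09-0.80) |

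Every reduced estimate stays inside the interval for the complete count.

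**Step 5. Cohort B.** These subjects stop drug at 52 weeks but stay on the on-study schedule (Section 3.5), where AEs are assessed continuously (Table 5.1-2). Subjects in Cohort A who stop move to Table 5.1-3. Ascertainment after last dose can therefore differ between the randomized cohorts, for which Section 8.4.3 reports onset and resolution separately.

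**The case against.** The best defence is that Section 3.6 is one sentence whose second half almost repeats the table. Read that way, the two agree. Section 6 independently requires serious and nonserious AEs to be followed to resolution or stabilization, and a table note does not cancel it. On this view nothing is lost.

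Part of this stands. Section 3.6 is ambiguous rather than flatly contradictory, and a site that reads Section 6 will keep following a not-related event. But if 3.6 only repeats the table, its mention of select AEs does no work, and both texts are then narrower than Section 6. The mismatch with Section 6 remains under either reading.

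A reader might infer more than the documents support:

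- **That not-related events disturb the primary incidence.** They cannot, because it counts treatment-related events only (Sections 8.3.1 and 8.4.2).
- **That late related events in general are lost to the primary endpoint.** Section 6.1.1 makes related SAEs reportable without time limit, which covers fatal and life-threatening events and those requiring hospitalization.
- **That sites do in fact differ.** This is a plausible consequence of the wording, but the documents do not state it.

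**Conclusion.** The point holds for the secondary objective and should be corrected. Under Table 5.1-3, outcomes of not-related high-grade select AEs open at day 100 may go unrecorded, and their time to resolution would then be censored at a contact that need not have asked about the event. The number of such subjects cannot be derived from the documents.

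The new-onset gap is smaller. For the primary incidence it is confined to related, nonserious Grade 3-4 events. For the secondary it also includes not-related events. The 1-to-6 range rests on an assumed late-onset share. For the primary it is an upper bound under that assumption, because related serious events must be reported anyway. For the secondary the base could be larger, because the 5% rate covers related events only. A few subjects is the likely order. This does not threaten the primary estimate overall, but it can be visible in a category with about six events.

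**What to change.** 1. Reconcile Sections 3.6, 6.1.1, 6.2.1 and Table 5.1-3 so that data on every Grade 3-5 select AE ongoing at day 100 are collected to resolution or stabilization, regardless of relationship.
2. State one rule, in the same four places, for recording select AEs that start after day 100: related or all, serious or also nonserious.
3. In Sections 8.4.2 and 8.4.3, report incidence over the period in which collection is complete, and list later-onset events separately.
4. Say how Cohort B's off-drug interval and any retreatment count towards that period. A bare cut-off at 100 days after last dose would not do, because it would discard late related events in never-retreated Cohort B subjects who are still under continuous AE assessment.

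The cost is wording in four places and the analysis text, plus some extra data collection. The 3-monthly contacts exist but are for survival status and may be by phone, so they would have to ask about each open select AE. Incidence may shift by a few events. Where past data cannot be recovered, the reporting period can still be fixed before the final analysis, which waits for five-year follow-up (Section 8.5).
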